5. SAMPLE SIZE

As this is a pilot study, a sample size of 90 (30 in each arm) subjects will be chosen as a convenience sample. This is the number estimated to enroll in a 24 week period.

6. STUDY POPULATION

Ninety (90) subjects contributing to approximately 120 to 200 crowns on primary teeth will be recruited from the patient pool of the Center for Pediatric Dentistry who receive care under general anesthesia and enrolled into the study. A maximum of four crowns will be placed in any subject. It is estimated that it will take approximately 24 weeks to place all crowns and complete the baseline examination.

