4. STUDY DESIGN

This pilot study is a single-center, non-blinded, controlled clinical trial with evaluations at baseline; follow up assessments at months 3, 6, 12 and 18; and a final assessment at the end of study visit occurring at 24.

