6.1 Inclusion Criteria

- Patients of record at the University of Washington's Center for Pediatric Dentistry
- Patients in general good health (ASA I)
- Patients aged 5 years old or younger
- Patients in need of at least one preformed crowns, on anterior primary teeth
- Patients undergoing general anesthesia for dental treatment
- Parent or guardian of patient able and willing to provide informed consent

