7.4 Treatment Randomization

Restorations will be randomly allocated to a patient; all teeth in a single patient will be randomly allocated to receive one of the restoration treatments: 1) NuSmile Signature crowns (thirty patients in the intervention group 2) NuSmile ZR crowns (thirty patients in the intervention group and 3) and composite strip crowns (thirty patients in control group).

The randomization sequence will be created using STATA 12.0 (StataCorp, College Station, TX) statistical software using random block sizes, which are known only to the study statistician. The randomization list will be created and placed in the order determined above into opaque sealed envelopes prior to trial start. The envelopes will be kept in a secure place known only to the study coordinator, research assistants, and statistician.

Each patient will be assigned a random treatment when they arrive at the treatment appointment and after they have been determined eligible and have signed the consent form. The clinician will be told the treatment assignment immediately prior to the treatment appointment.

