7.5 Operative Procedures

After the subject's parent/guardian has provided informed consent for participation in the study, patient's sedated procedure will be accomplished. This study will be executed within a comprehensive restorative treatment. A rubber dam will be placed and the crowns will be placed following manufacturers' guidelines, see below.

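### When a child needs more than four crowns, no rule fixes which teeth are study teeth before the arm is revealed

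*Combined protocol and SAP*

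**What the plan says.** All references are to the combined protocol and SAP.

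- **Cap.** Section 6 (Study Population): "A maximum of four crowns will be placed in any subject". The same section expects "Ninety (90) subjects contributing to approximately 120 to 200 crowns on primary teeth".
- **Eligibility.** Section 6.1 sets a floor and no ceiling: "Patients in need of at least one preformed crowns, on anterior primary teeth". No exclusion in Section 6.2 concerns the number of affected teeth.
- **Allocation.** Section 7.4 randomizes by child: "all teeth in a single patient will be randomly allocated to receive one of the restoration treatments". On timing: "Each patient will be assigned a random treatment when they arrive at the treatment appointment and after they have been determined eligible". And: "The clinician will be told the treatment assignment immediately prior to the treatment appointment".
- **Blinding.** Section 4 describes a "single-center, non-blinded, controlled clinical trial".
- **Setting.** Section 7.5: "This study will be executed within a comprehensive restorative treatment".
- **Which teeth are followed.** Section 7.5.4 applies intention-to-treat to randomized teeth, but no step draws up a list of them. Section 10 asks for baseline photographs of the selected teeth without saying how, when or by whom they are selected.

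**The concern.** A child with five or six qualifying anterior teeth is eligible, but at most four crowns may be placed. Someone has to decide which teeth those are. The sealed envelopes hide the arm while children are being enrolled. They do not protect the choice of teeth if it is made after the envelope is opened.

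There is a plausible reason for the choice to differ by arm. Section 7.5.2 gives the three crown types different overall reductions (25-30%, 20-25% and 15-20%) and different margin levels. An operator who knows the arm could quite reasonably favor different teeth for different crowns. If sounder teeth enter one arm and more damaged teeth another, retention, fit, marginal adaptation and pulp outcomes will differ for reasons unrelated to the crown.

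The planned analysis would not repair this. The GEE models in Section 11 allow for correlation between teeth in one mouth, not for selection of teeth. The intention-to-treat rule covers only teeth already counted as randomized. A qualifying tooth that was never chosen leaves no outcome data.

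**Working it through.** **Inputs.** 90 children, 30 per arm (Section 5); 120 to 200 crowns and a cap of four (Section 6); at least one crown per child (Section 6.1, and the definition of enrolled subjects in Section 11).

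**1. The plan's own figure.** 3 × 30 = 90 agrees. It is a convenience sample with no power calculation, so there is no derived sample size to reproduce, and this point changes none.

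**2. Crowns per child.** 120/90 = 1.33 and 200/90 = 2.22. If every child were at the cap the total would be 4 × 90 = 360.

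**3. How many children can be at the cap.** If k children have four crowns and the other 90 − k have at least one, then 4k + (90 − k) ≤ C, so k ≤ (C − 90)/3.
- C = 120: k ≤ 30/3 = 10 children (11%).
- C = 200: k ≤ 110/3 = 36.7, so 36 children (40%).

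If a child needing more than four receives four, such children are a subset of these.

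**4. An illustrative distribution of need (assumption).** Let need follow a zero-truncated Poisson, fitted so that the mean of min(need, 4) equals C/90.
- C = 120: parameter 0.61, P(need > 4) = 0.09%, or about 0.1 child in 90.
- C = 200: parameter 1.99, P(need > 4) = 6.0%, or about 5 children in 90.

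**5. Illustrative size of the bias (assumed risks).** Take a child with six qualifying teeth, four with a 10% failure risk and two with 30%.
- Arm-blind choice of four: expected failure (4 × 10% + 2 × 30%)/6 = 16.7%.
- The four soundest teeth: 10%.
- Spurious difference if one arm chooses the soundest and the other chooses blindly: 6.7 points within such children.

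The trial-wide effect is 6.7 points times the share of crowns these children supply:

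| Scenario | Share of crowns | Effect |
|---|---|---|
| Poisson model, 200 crowns, 5 children | 20/200 = 10% | 0.7 points |
| All 10 possible capped children, 120 crowns | 40/120 = 33% | 2.2 points |
| All 36 possible capped children, 200 crowns | 144/200 = 72% | 4.8 points |

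The last two rows require every capped child to have six qualifying teeth and the selection to be complete. The 6.7 is not a strict maximum. If the other arm took its four worst teeth, their risk would be (2 × 10% + 2 × 30%)/4 = 20%, the gap would be 10 points, and the rows would become 1.0, 3.3 and 7.2.

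**6. Order of events.** Screening against Section 6 comes before enrollment (Section 7.3). The arm is assigned on arrival for treatment, the clinician is told, and treatment follows (Section 7.4). No section places the identification of study teeth anywhere in this order.

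**The case against.** **The passages contradict each other.** A reader might infer that the cap, the allocation of all of a child's teeth and the comprehensive-treatment setting cannot all be followed. That is too strong. Section 7.4 can be read as setting the unit of randomization (one crown type per child), Section 6 as limiting how many crowns are placed, and Section 7.5 as describing the setting. The clash arises only if Section 7.4 is read as covering every tooth that needs a crown. The wording needs reconciling, but the selection gap exists under either reading.

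**The operator chooses.** A reader might also infer that the treating clinician picks the teeth with the arm known. No section names a selector. Screening precedes assignment, several Section 6.2 criteria are tooth-level and can be judged then, and the wording of Section 7.5.4 suggests that teeth are identified at randomization. This stands: arm-aware selection is permitted, not established. Equally, nothing requires the teeth to be fixed or recorded earlier.

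**Few children are affected.** This largely stands. Section 1 says that mandibular incisors are generally protected and maxillary incisors exposed, and the four maxillary incisors match the cap. Supposing that 20% of children exceed the cap would be unsupported. It means 18 children and at least 18 × 4 + 72 = 144 crowns, which is impossible at the 120-crown end of the range.

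**The bias is lost in the noise.** With about 200/3 = 67 crowns per arm and an assumed 10% failure risk, the standard error of a difference is √(2 × 0.10 × 0.90/67) = 5.2 points before clustering. The Poisson-based 0.7 points is well inside that. The 30% risk may also be high, because Section 6.2 already excludes teeth without facial or lingual walls and teeth expected to be lost within a year. These arguments lower the urgency. They do not supply the missing rule, and systematic bias does not average out as random error does.

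**Conclusion.** The concern holds in a limited form. The plan admits children with more than four qualifying anterior teeth and caps crowns at four. It does not say which teeth are then studied, or that they are recorded before the arm is known. In an unblinded trial where the clinician is told the arm before treating, this leaves room for arm-aware selection of teeth.

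The direct bias is probably small. The bound of 10 to 36 children at the cap rests on Section 6's crown totals and on at least one crown per child. The 0.7 to 4.8 points (1.0 to 7.2 with opposite selection in the other arm) rest on assumed failure risks, and the larger values on an extreme pattern of need. The documents give neither failure risks nor the distribution of need, so the true size cannot be calculated. Because unchosen qualifying teeth are not recorded, the planned data could not show afterwards whether selection had occurred.

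**What to change.** 1. At the eligibility check before allocation, list the study teeth by tooth number on the screening form. If more than four qualify, select four by a preset arm-blind rule, for example a fixed or random tooth-number order, and record all qualifying teeth. Open the envelope only after the list is complete.
2. Use this list as the denominator for the intention-to-treat rule in Section 7.5.4. Tooth exclusions that arise later, such as extraction or the wall criterion in Section 6.2 that is judged after preparation, can then be counted and compared by arm. This helps in every child, not only those above the cap.
3. Ask the sponsor to reconcile the cap in Section 6 with Section 7.4 and Section 7.5, including what applies to teeth beyond four. How many crowns a child may receive, and how the remaining teeth are managed, is for the sponsor to settle.

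The cost is one entry on the screening form and a short clarification of the text, with no extra children, visits or staff. The small downside is that some listed teeth will prove unrestorable under anesthesia and must be accounted for.

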6.1 Inclusion Criteria

- Patients of record at the University of Washington's Center for Pediatric Dentistry
- Patients in general good health (ASA I)
- Patients aged 5 years old or younger
- Patients in need of at least one preformed crowns, on anterior primary teeth
- Patients undergoing general anesthesia for dental treatment
- Parent or guardian of patient able and willing to provide informed consent

6.2 Exclusion Criteria

- Medically compromising condition
- Teeth with proximal space closures of sufficient magnitude to preclude placement of crown
- Teeth with complete absence of facial or lingual walls following tooth preparation
- Teeth that are expected to be exfoliated/extracted within one year will not participate in the study
- Anterior crowding
- Occlusion class III

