7.5.2 Preparation of the tooth

A) For NuSmile PVSCC Signature Crowns:

The tooth should be prepared to fit the crown so that the crown fits the tooth passively without using pressure. The incisal length of the tooth is reduced by approximately 2mm with the interproximal contacts opened. A feather-edge margin is created as far subgingivally as possible (approximately 1-2mm). The tooth is overall reduced by approximately 25-30%. For preparing the tooth subgingivally, and refining the preparation, tapered diamond burs may be used, proceeding from coarse to fine as the preparation is completed.

B) For NuSmile ZR Crowns:

The tooth should be prepared to fit the crown so that the crown fits the tooth passively without using pressure. The incisal length of the tooth is reduced by approximately 1.5-2mm with the interproximal contacts opened. With a coarse tapered bur, the tooth is overall reduced supragingivally by approximately 20-25%, or 0.5-1.25mm on all planes of the tooth. Reduction should follow the natural contours of the clinical crown and meet in a thin, tapered incisal edge. Carefully extend and refine the preparation margin to a feather-edge approximately 1-2mm subgingivally with a thin tapered diamond bur (green stripe 6852-012). Check that no subgingival ledges remain. Round all line angles and point angles of prepared teeth.

C) For Strip Composite Crowns:

The celluloid crown is selected based on the mesiodistal width of the tooth. The incisal length of the tooth is reduced by approximately 2mm with the interproximal contacts opened. A feather-edge margin is created supra or at gingival level. The tooth is overall reduced by approximately 15-20%. For preparing the tooth, and refining the preparation, tapered diamond or tungsten carbide burs may be used.

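### Teeth can be excluded after allocation under criteria whose effect may differ by arm, and the plan requires no count of them by arm

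*Combined protocol and SAP*

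**What the plan says.** Section 7.3 has every subject screened against the Section 6 criteria before enrolment. Section 7.4 keeps that order: "Each patient will be assigned a random treatment when they arrive at the treatment appointment and after they have been determined eligible". The unit of allocation is the child: "all teeth in a single patient will be randomly allocated to receive one of the restoration treatments". The operator then learns the arm: "The clinician will be told the treatment assignment immediately prior to the treatment appointment". Section 4 describes the design: "This pilot study is a single-center, non-blinded, controlled clinical trial".

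One exclusion in Section 6.2 is worded by the condition of the tooth once it has been prepared: "Teeth with complete absence of facial or lingual walls following tooth preparation". Preparation is part of the allocated treatment. In Section 7.5.2 the Signature text reads "The tooth is overall reduced by approximately 25-30" per cent; the figures for the ZR and strip crowns are 20-25% and 15-20%.

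Section 7.5.4 treats two situations differently. A randomised tooth that will not take its crown, and gets a composite crown instead, stays in under intention-to-treat with the reason recorded. A tooth that needs extraction leaves the trial, with a parenthesis tying this to failure to match the eligibility criteria.

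Section 11.0 omits missing data, treats a subject as enrolled once at least one crown has been placed, and asks for no tally of teeth removed after allocation.

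**The concern.** Randomisation makes the arms comparable for the teeth that were allocated. If some of those teeth are then removed for a reason that the assigned preparation can influence, the teeth left in each arm may no longer be alike. A tooth with little remaining wall is plausibly one with a poorer outlook, so removing more of these from one arm could make that arm look better with no difference between the crowns. This needs no biased judgement, because a different amount of reduction could be enough.

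The second part is traceability. Without counts and reasons by arm, a reader of the results could neither detect such a difference nor rule it out. A randomised child whose only study tooth was excluded would also fall outside the Section 11.0 definition of enrolled.

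**Working it through.** **Order of events.** Screening (7.3), then eligibility and consent, assignment on arrival, disclosure of the arm (7.4), preparation (7.5.2), fitting or failure to fit (7.5.3, 7.5.4). The wall criterion in 6.2 refers to a point after preparation, which is after disclosure. The extraction rule in 7.5.4 also acts on randomised teeth.

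**Overlap.** A tooth that loses a wall on preparation may also be one that will not take the crown. Section 6.2 would then exclude it and Section 7.5.4 would keep it. No section says which governs.

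**Records.** Section 7.5.4 asks for a reason for fitting failures only. Section 10 asks for a justification when a tooth or crown is lost to trauma, which is a different event. Section 11.0 asks for nothing on exclusions.

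**Size.** The plan gives no figure to reproduce here, because the sample of 90 is a convenience sample. The inputs from the documents are 90 children in three arms of 30, "Ninety (90) subjects contributing to approximately 120 to 200 crowns on primary teeth", and "A maximum of four crowns will be placed in any subject". This gives 120/3 = 40 to 200/3 = 67 teeth per arm, and 120/90 = 1.33 to 200/90 = 2.22 teeth per child. Every rate below is an assumption.

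Let the crowns be equally good, with a share s of teeth weak. Weak teeth fail at f1 = 40% and the rest at f0 = 10%. A share e of the weak teeth, and no others, is excluded.

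Observed failure = [s(1−e)f1 + (1−s)f0] / [s(1−e) + (1−s)]

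| s | e, arm A v B | All teeth excluded | Observed failure | Gap (points) |
|---|---|---|---|---|
| any | equal | equal | equal | 0 |
| 0.10 | 0.2 v 0.1 | 2% v 1% | 12.4% v 12.7% | 0.3 |
| 0.30 | 0.2 v 0.1 | 6% v 3% | 17.7% v 18.4% | 0.7 |
| 0.30 | 0.5 v 0.3 | 15% v 9% | 15.3% v 16.9% | 1.6 |
| 0.30 | 0.5 v 0 | 15% v 0% | 15.3% v 19.0% | 3.7 |
| 0.50 | 0.5 v 0 | 25% v 0% | 20.0% v 25.0% | 5.0 |
| 0.50 | 1 v 0 | 50% v 0% | 10.0% v 25.0% | 15.0 |

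Swapping the arms reverses the sign.

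A second form gives the same message. Let true failure be p = 20%, with x = 15% of teeth excluded in one arm only, and let the excluded teeth have failure rate f. Observed failure is (p − xf)/(1 − x). With f = 100% it is 5.9% (gap 14.1 points), with f = 50% it is 14.7% (5.3 points), and with f = 20% it is 20% (0).

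**Scale.** At 19% failure, the standard error of a two-arm difference is √(2 × 0.19 × 0.81 / m): 8.8 points at m = 40 and 6.8 at m = 67. With design effect 1 + (k − 1)ρ and ρ = 0.5, k = 1.33 gives 1.17 and 9.5 points, and k = 2.22 gives 1.61 and 8.6 points.

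**Children.** Take the 120 to 200 crowns as teeth allocated and let exclusions be independent with probability q. The expected number of children with every study tooth excluded is n1·q + n2·q² + n3·q³ + n4·q⁴, where nj is the number of children with j teeth. At q = 6%, over all possible splits, it is 3.7 to 4.8 of 90 at 120 teeth and 0.3 to 3.2 at 200. Positive correlation within a child would raise these counts.

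**Excluded teeth counted as failures.** The rate is s(1−e)f1 + (1−s)f0 + se. At s = 0.30, exclusion of 6% v 3% gives 22.6% v 20.8% (1.8 points), and 15% v 0% gives 28.0% v 19.0% (9.0 points). Both gaps run in the opposite direction to those in the table.

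**The case against.** The strongest reply is that the plan already fixes eligibility first. Section 7.3 applies all of Section 6 before enrolment, so the wall criterion could be meant as a pre-operative expectation. The extraction clause, with its qualifier, could mean only teeth that were never eligible, under a rule worded alike for all arms. Both readings are possible. Neither removes the literal wording of Section 6.2, and Section 7.3 makes the disagreement over timing plainer.

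Next, nothing in the documents links the reduction percentages to complete loss of a wall, so arm dependence is a possibility and has not been shown. That stands. It also stands that most of the illustrative gaps are below one standard error, and that this is a pilot with no power claim. However, Section 11.0 plans inferential comparisons between arms, and how many allocated teeth cannot be restored as assigned is something a pilot ought to report.

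A reader might go further and infer that the treating clinician, knowing the arm, will remove teeth selectively. The documents do not support this, because no section says who decides an exclusion. Nor do they support the charge that intention-to-treat is simply abandoned: Section 7.5.4 keeps fitting failures and writes extraction as an explicit exception.

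**Conclusion.** The point holds as one about timing and reporting. Sections 6.2, 7.3, 7.4 and 7.5.4 do not agree on when a tooth's eligibility is settled. As written they allow exclusion after allocation that can depend on the arm, and nothing requires such exclusions to be counted by arm.

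Size and direction cannot be derived from the documents. The bias is zero if exclusions are equal across arms or unrelated to prognosis. Under the assumed rates it runs from under 1 point to about 15, against a standard error of about 7 to 9.5 points (19% failure, intra-child correlation 0 to 0.5). Neither end of that range is a bound. The 15 needs half of all teeth excluded in one arm and none in another, or, in the second form, a gap of 14.1 needs every excluded tooth to have been a failure. A reader might infer from the reduction figures that a particular arm is favoured, but the documents give no basis for a direction.

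**What to change.** Reconcile Sections 6.2, 7.3, 7.4, 7.5.4 and 11.0 so that:

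1. Each tooth's eligibility for the study is settled and recorded before the envelope is opened.
2. Every tooth allocated after that and given any study restoration, including a composite crown after failure to fit, is analysed in its randomised arm in the Section 11.0 between-arm comparisons. This applies even if the tooth meets the post-preparation wall criterion, whose finding can still be recorded as data.
3. Allocated teeth with no study restoration, and allocated children with no crown placed, are reported by arm with reasons. One sensitivity analysis of retention counts such teeth as failures, identically in all arms. They need a category of their own, because Appendix 8 has no code for a tooth that was never crowned.

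The cost is one form line per tooth, one table by arm and a few sentences in five sections. Assignment stays on arrival. Some pre-operative judgements will prove wrong, and those teeth then fall under item 2 or 3. The sensitivity analysis can overstate a difference, as the 1.8 and 9.0 points with equal crowns show, so it should be read beside the main comparison and not in place of it. These changes concern study data only. The clinical handling of any tooth is not addressed.

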7. STUDY PROCEDURES

7.1 Training

All research study team members will obtain clinical research and HIPAA training prior to start of study. All pediatric dental (PEDO) clinician team who work at the Dental Surgery Center (DSC) and are willing to participate in this study will train with the NuSmile crowns by preparing extracted or typodont primary teeth and cementing the crowns and at least six *in vivo* cases done under general anesthesia for each crown type in the study. Intra and inter-reliability assessment will be obtained ($\text{Kappa} > 0.8$). Training and calibration will be performed by a representative from NuSmile and [name] from the Center for Pediatric Dentistry.

